11 STUDY TREATMENT EXPOSURE AND TREATMENT COMPLIANCE

A summary of exposure related to Roflumilast cream and the vehicle will be presented using the safety population by treatment group. It will include descriptive statistics on the number of days on IP, as well as the number of investigational product applications based on diary, for each treatment group. The number of days on IP, will be calculated as follows:

	STATISTICAL ANALYSIS PLAN, Version 1.0
Protocol Number: ARQ-151-312	Sponsor: Arcutis Biotherapeutics, Inc.

[(last treatment date- first treatment date) + 1].

For each subject, investigational product application compliance (%) will be calculated as follows:

 $\frac{\text{Number of investigational product applications}}{\text{Number of expected investigational product applications}} \times 100$

Number of investigational product applications will be calculated as number of expected investigational product applications minus number of doses missed. Number of doses missed and the date that the dose was missed were collected in eCRF.

Number of expected investigational product applications will be calculated as calculated as last treatment/interruption date - first treatment date + 1. If latest treatment date \ge latest interruption date, then the latest treatment date will be used; otherwise, latest interruption date will be used in deriving the expected number of IP applications.

Descriptive statistics for the compliance as well as the number of missed applications, subjects with < 80%, [80% - 100%], and >100% compliance will be presented by treatment. Furthermore, the incidence of subjects who missed more than 3 consecutive doses and compliant subjects will be presented by treatment.

A subject will be considered compliant with the dosing regimen if the subject meets both of the following requirements:

- applies at least 80% of the expected applications during the study drug application period
- does not miss more than 3 consecutive doses

Total weight of study medication applied (determined by weighing the study medication before and after use) will be summarized by treatment using descriptive statistics. Weight of study medication used will be documented in source documents and in eCRF. Total weight of IP used is determined by subtracting minimum of (returned, remained) tube weight from the maximum of (dispensed, prepared) tube weight for each tube that was dispensed and summing the weights. Calculate Actual IP Used: maximum of (dispensed, prepared) tube weight minus minimum of (returned, remained) tube weight = grams

If a tube is not returned at the end of the study or a tube weight is missing, actual IP used for the tube and total weight of IP applied during study will be missing.

Number of days on IP and compliance, including compliance collected at each clinic visit, will be displayed in a listing of study treatment administration by subject, for each treatment. A listing of

	STATISTICAL ANALYSIS PLAN, Version 1.0
Protocol Number: ARQ-151-312	Sponsor: Arcutis Biotherapeutics, Inc.

drug accountability including the kit number, tube number, dispensed and returned weight will also be provided.

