4.8.5. Treatment Compliance

Investigational product tubes will be weighed at each clinic visit.

Subjects/caregivers will complete a daily diary recording the date and time of each dose applied, any missed doses, and a comment section should the subjects have a comment, e.g., record potential AEs. Site personnel will review the diaries and use the information to question the subject regarding compliance and AEs and then record appropriate information in source documents and complete Case Report Forms (CRFs). If a subject misses a dose, they should be instructed to return to the protocol investigational product administration schedule (i.e. if subject forgets a dose they should wait until that evening and apply as usual).

A subject will be considered compliant with the dosing regimen if the subject meets both of the following requirements:

- applies at least 80% of the expected applications during the study drug application period
- does not miss more than 3 consecutive doses

Compliance will be assessed by review of the dosing diary. Weight of investigational product applied (via dispensed and returned tube weights) will be measured for reporting purposes.

If the diary shows less than 80% of expected daily applications (but not more than 3 consecutive missed doses), the subject is using too little study drug and retraining must be conducted and documented.

Compliance will be documented in source and in eCRF.

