6.5. Study Medication Compliance

The number of study drug applications by each subject based on diary data will be summarized using summary statistics (mean, standard deviation [SD], median, minimum, and maximum), and categorically.

The number of investigational product applications by each subject based on diary data will be summarized using descriptive statistics.

The amount of investigational product used by each subject based on tube weight will be summarized by treatment using descriptive statistics, and categorically.

Investigational product application compliance will be calculated based on number of applications divided by the expected number (amount) of investigational product applications for each subject. Compliance will be summarized descriptively by treatment group.

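### SAP 11 derives applications as expected minus missed doses, so compliance is capped at 100%, extra applications cannot appear, and the planned row above 100% is empty by construction

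*SAP*

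**What the plan says.** SAP section 11 defines compliance as the number of applications divided by the number expected, times 100. It describes the number of applications in the exposure summary as diary-based, then gives the derivation: "Number of investigational product applications will be calculated as number of expected investigational product applications minus number of doses missed". The subtracted term comes from the case report form: "Number of doses missed and the date that the dose was missed were collected in eCRF". The expected number is one per calendar day, "last treatment/interruption date - first treatment date + 1". The results are then to be grouped: "subjects with < 80%, [80% - 100%], and >100% compliance will be presented by treatment".

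A subject is called compliant if two conditions hold. The first is that the subject "applies at least 80% of the expected applications during the study drug application period"; the second is that no run of more than three doses was missed. SAP section 4.3 applies the 80% requirement again as an entry condition for the Per Protocol population.

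Protocol section 4.8.5 says subjects or caregivers "will complete a daily diary recording the date and time of each dose applied, any missed doses". Protocol section 6.5 says: "The number of study drug applications by each subject based on diary data will be summarized".

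**The concern.** The SAP labels as a number of applications something that is really the number of calendar days less the number of recorded misses. That matters in two ways.

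First, the table has a category for over-application that the formula cannot populate. A zero in that row, in both arms, would be read as a finding that nobody over-applied, when no other result is possible.

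Second, the derivation treats every day as dosed unless somebody has entered a miss. Missing documentation that is not turned into a missed-dose entry raises reported compliance rather than lowering it or showing up as unknown. The same percentage decides part of the membership of the Per Protocol population.

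**Working it through.** **Inputs**

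- E, expected applications: one per day from first treatment to last treatment or interruption (SAP 11). SAP 3.3 plans once-daily dosing for 28 days, plus or minus 3, so E is about 25 to 31 for a completer.
- M, missed doses: a count from the eCRF, so M ≥ 0 (SAP 11).
- Threshold: 80% (SAP 11 and 4.3).
- In-clinic applications: Day 1, Week 1 and Week 2, so three (Protocol and SAP visit schedules).

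The plan states no figure to reproduce. The check is on the formula itself.

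**Step 1: the cap.** Compliance C = 100 × (E − M)/E = 100 × (1 − M/E). Since M ≥ 0, C ≤ 100. Evaluating every E from 1 to 60 and every M from 0 to E gives a maximum of exactly 100.0%, reached at M = 0. No subject can fall in the category above 100%.

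**Step 2: where the 80% cut falls under the rule.**

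- E = 25: 5 recorded misses give 20/25 = 80.0% (pass); 6 give 19/25 = 76.0% (fail).
- E = 28: 5 give 23/28 = 82.1% (pass); 6 give 22/28 = 78.6% (fail).
- E = 31: 6 give 25/31 = 80.6% (pass); 7 give 24/31 = 77.4% (fail).

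**Step 3: the rule against a direct count, E = 28.** The scenarios are assumptions chosen to show the mechanism; the documents give no frequencies. The last two rows assume that no undocumented day is entered as missed.

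| Recorded missed | Undocumented days | Extra applications | SAP rule | Documented applications / E |
|---|---|---|---|---|
| 0 | 0 | 3 | 28/28 = 100.0% | 31/28 = 110.7% |
| 3 | 0 | 3 | 25/28 = 89.3% | 28/28 = 100.0% |
| 0 | 6 | 0 | 28/28 = 100.0% | 22/28 = 78.6% |
| 3 | 10 | 0 | 25/28 = 89.3% | 15/28 = 53.6% |

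The first row could arise if a subject dosed in clinic and again that evening on each of the three clinic-application days. The third and fourth rows cross the 80% line: the subject passes under the rule and fails on documented doses. On the same assumption, a run of four or more blank days would also satisfy the consecutive-miss condition, because no miss is on record.

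**The case against.** Four points can be made for the plan.

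**Site review.** Missed doses come from the eCRF, not straight from the diary. Under Protocol 4.8.5, site staff review the diary, question the subject about compliance and then complete the CRF. A blank day may well be resolved and entered as missed. The visit schedules also refer compliance determination to an IP Handling Manual that is not among the documents. This stands. A reader might infer that a lost or blank diary necessarily scores 100%, but the documents neither require nor exclude entry of blank days as missed.

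**Tube weight.** Tubes are weighed at each visit, and use well away from that expected for the affected area prompts retraining (Protocol 4.8.4). SAP 11 summarises total weight by arm and lists dispensed and returned weights. So over-use is not hidden from the trial as a whole, and heavy over-application would be expected to show there. The backup is partial, however: SAP 11 never compares weight used with weight expected, and it sets a subject's total to missing if one tube is unreturned or unweighed.

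**Consistency with the protocol.** A reader might infer that the subtraction rule is an undeclared departure, because SAP 3.5 does not list it. The documents do not support that. The protocol supplied is marked as the original, while SAP section 1 says the SAP is based on Amendment 3, whose compliance wording is not available here. Moreover, the diary records missed doses too, so subtraction is one way of using diary data.

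**Small consequence.** Over-application could not fail a cut that only sets a minimum. The Per Protocol analyses are observed-data sensitivity analyses, one for the primary endpoint and one for the Moderate-population endpoint. This also stands.

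None of these points makes the category above 100% reachable.

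**Conclusion.** The concern holds in a limited form. That the percentage is capped, that extra applications cannot enter the application count, and that the top category must be empty all follow from SAP 11 alone, with no outside assumption beyond a missed-dose count not being negative.

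The effect on the 80% cut is conditional. It arises only for undocumented days that sites do not enter as missed, and the number of such days is unknown. If all blank days were entered as missed, the rule and a documented-dose count would agree for subjects with no extra applications.

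What is affected is the exposure and compliance tables and, conditionally, membership of the Per Protocol populations. It would be wrong to infer that the efficacy conclusions are at risk: the primary and multiplicity-controlled analyses use the ITT, Moderate ITT and WI-NRS populations, none of which depends on compliance. The rule should still be corrected, because as written it yields a zero for over-application that carries no information.

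**What to change.** **If dated dose records are available**, define the number of applications in SAP 11 as the count of unique documented applications from the diary and the clinic, each dose counted once. Removing duplicates matters. If clinic doses are also written in the diary, adding the two sources would give a fully adherent subject (28 + 3)/28 = 110.7%, a false entry above 100%. Show days with neither a dose nor a missed-dose entry as a separate, not-documented category. State how such days are treated for the 80% cut and the consecutive-miss condition.

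**If the eCRF holds only missed doses**, delete the row above 100%. State that diary compliance is capped at 100% and cannot detect over-application, and report over-use from the tube weights already collected against expected weight. Say whether sites enter blank diary days as missed.

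The cost is SAP wording and one derivation, settled before unblinding. The first option may need a transfer of existing diary data, and reported compliance may fall somewhat. Neither option asks anything more of subjects.

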4.8.6. Removal of Subjects from Study Treatment

Subject treatment with study drug in this trial may be discontinued for any of the following reasons:

- 1. Occurrence of any medical condition or circumstance that, in the opinion of the Investigator does not allow the subject to adhere to the requirements of the Protocol.
- 2. Adverse Events as described in Section 5.1.12 and Section 5.9. The Investigator must follow the subject until the AE resolves or satisfactorily stabilizes.
- 3. Treatment must be discontinued immediately in the event of a female subject's pregnancy.
- 4. Subject's decision to discontinue treatment with study drug.
- 5. C-SSRS (Section 5.1.10) indicative of suicidal ideation
- 6. PHQ-8 (Section 5.1.7) or modified PHQ-A (Section 5.1.8) score ≥15 if determined by Investigator in consultation with mental health professional
- 7. CDI-2 (Section 5.1.9) raw total score of \geq 32 if determined by Investigator in consultation with mental health professional
- 8. Requirement for use of prohibited concomitant medication after consultation with the Sponsor and Medical Monitor.
- 9. Subject's repeated failure to comply with protocol requirements or study related procedures.
- 10. The subject interrupts trial study drug application for more than 50% of scheduled doses.
- 11. Termination of the study by the Sponsor, FDA, or other regulatory authorities.

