4.8.7. Removal of Subjects from the Study

A subject may be removed from study participation for any of the following reasons:

- Subject death.
- Subject's decision to withdraw from the study.
- Subject is lost to follow-up. A subject will be considered lost to follow-up after three phone and three email attempts and documentation of a certified letter sent to the subject's address.
- Termination of the study by the Sponsor, FDA, or other regulatory authorities

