4.3 Per Protocol (PP) Population

Per protocol population will include all subjects who are randomized, at least 80% compliant with study medication application, have a vIGA-AD assessment within the Week 4 visit window and show no "major deviations" from the study protocol that would affect the interpretation of efficacy. A complete list of major deviations from the study protocol will be created prior to unblinding and include a list of all subjects who will be excluded due to those major deviations. See section 7.2 for more details.

All subjects will be analyzed according to the actual treatment group they received and the stratum they belong to. Actual and randomized treatment will only differ if the subject received the wrong treatment throughout their participation in the study.

4.4 vIGA-AD Moderate ITT Population

vIGA-AD Moderate ITT population will be a subset of the ITT population with vIGA-AD score (randomized score) 'Moderate' at randomization.

All subjects will be analyzed according to the treatment group and the stratum to which they were randomized.

4.5 vIGA-AD Moderate PP Population

vIGA-AD Moderate PP population will be a subset of the PP population with vIGA-AD score (actual score) 'Moderate' at randomization.

	STATISTICAL ANALYSIS PLAN, Version 1.0
Protocol Number: ARQ-151-312	Sponsor: Arcutis Biotherapeutics, Inc.

All subjects will be analyzed according to the actual treatment group they received and the stratum they belong to. Actual and randomized treatment will only differ if the subject received the wrong treatment throughout their participation in the study.

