13.1 Adverse Events

Adverse events (AEs) will be coded according to the latest available version of Medical Dictionary for Regulatory Activities (MedDRA) (Version 23.0 or higher).

Treatment emergent adverse events (TEAEs) are defined as any AEs with onset on or after the first study drug application. See Appendix 2 for handling of completely or partially missing dates for AEs. In the case where it is not possible to define an AE as treatment emergent or not, the AE

	STATISTICAL ANALYSIS PLAN, Version 1.0
Protocol Number: ARQ-151-312	Sponsor: Arcutis Biotherapeutics, Inc.

will be classified as treatment emergent. All reported TEAEs will be summarized by treatment group.

Overall summary will be presented, which will include the total number of events, and the number and percentage of subjects who experienced TEAE, TEAE by the strongest relationship, TEAE by the maximum severity, treatment-related TEAE by maximum severity, treatment-emergent serious AE (TESAE), treatment-emergent Non-SAE, TEAE leading to study treatment discontinuation, TEAE leading to study discontinuation, TEAE on an application site, and TEAE leading to death.

The number and percentage of subjects who experience TEAE will be summarized by SOC and PT within SOC. In addition, similar table will be presented by treatment groups for age 6 to 17 years and ≥ 18 years separately. Unless otherwise specified, a subject experiencing the same TEAE multiple times will be counted only once for the corresponding PT. Similarly, if a subject experiences multiple TEAEs within the same SOC, the subject will be counted only once for that SOC. TEAEs will be sorted alphabetically by SOC and within each SOC the PT will be presented by descending frequency in the safety analysis set. A treatment-related TEAE is defined as any TEAE that is assessed by the Investigator as likely, probably, or possibly related to study treatment. TEAE that is assessed as unrelated or unlikely will be defined as not treatment-related. If a subject experiences more than one TEAE within different relationship categories within the same SOC/PT, only the worst case (the strongest relationship) will be reported. TEAE with an unknown relationship will be considered as treatment-related.

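### SAP 11 counts expected applications only up to the subject's own last treatment or interruption date, so an early permanent stop can pass the 80% Per Protocol cut depending on how it is recorded

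*SAP*

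**What the plan says.** SAP Section 11 gives the denominator as "Number of expected investigational product applications will be calculated as calculated as last treatment/interruption date - first treatment date + 1". The end date is the latest treatment date unless an interruption is dated later; "otherwise, latest interruption date will be used in deriving the expected number of IP applications". The numerator comes from the same quantity: "Number of investigational product applications will be calculated as number of expected investigational product applications minus number of doses missed". On the source of the misses it says "Number of doses missed and the date that the dose was missed were collected in eCRF".

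SAP 4.3 admits to the PP set randomized subjects who are "at least 80% compliant with study medication application, have a vIGA-AD assessment within the Week 4 visit window" and who have no major deviation affecting the interpretation of efficacy. SAP 4.5 takes the Moderate-PP set from it. SAP 11 is the only place where the SAP defines a compliance percentage. SAP 3.3 plans once-daily treatment for 28 days, plus or minus 3.

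The plan separates stopping the cream from leaving the study. Protocol 4.8.6 lists "Subject's decision to discontinue treatment with study drug" as a reason to end treatment, and Protocol 4.8.7 separately lists "Subject's decision to withdraw from the study". SAP 13.1 tabulates "TEAE leading to study treatment discontinuation, TEAE leading to study discontinuation" as distinct items.

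**The concern.** An 80% cut for a PP set is meant to keep subjects who took most of the planned treatment. Here the denominator shrinks with the treatment actually taken, so a subject who used the cream without a miss for a week or two and then stopped can look fully compliant.

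The interruption clause corrects this only if two things hold: the date used is the end of the unresumed stop, and every day after the stop is logged as missed. SAP 11 states neither, and it has no rule for a permanent stop.

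Such subjects are provided for in the plan. Protocol 4.8.3 ends treatment after an unblinding but follows subjects to study completion, and SAP 12.1.1 names treatment discontinuation as an intercurrent event handled by treatment policy. A Week 4 assessment on Day 26 to 32 lies inside both the schedule's 3-day visit window and the Day 23 to 43 analysis window, so the point does not depend on which one SAP 4.3 means.

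At stake are the meaning of the PP and Moderate-PP sensitivity analyses and of the 80% to 100% row of the compliance table.

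**Working it through.** The plan states no computed figure to reproduce; 80% is a threshold.

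**Inputs.** The formula is from SAP 11, the 80% cut from SAP 4.3 and the 28 planned days from SAP 3.3. SAP 3.2, footnote m, says no application is made in clinic at the Day 29 visit, so that visit follows 28 planned applications.

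**Present rule.** E = later of (last treatment, latest interruption) − first treatment + 1. Compliance = (E − misses)/E.

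Take a subject who applies every dose from Day 1 to Day d and then stops for good. The three records below are assumed patterns, each compatible with the SAP wording.

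| Stop after Day | Last treatment date only, no misses | Interruption dated next day, one miss | Interruption to Day 28, all later days missed |
|---|---|---|---|
| 7 | 7/7 = 100% | 7/8 = 87.5% | 7/28 = 25% |
| 14 | 14/14 = 100% | 14/15 = 93.3% | 14/28 = 50% |
| 22 | 22/22 = 100% | 22/23 = 95.7% | 22/28 = 78.6% |
| 23 | 23/23 = 100% | 23/24 = 95.8% | 23/28 = 82.1% |

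- Between the first and third records, the 80% verdict reverses for every stop from Day 1 to Day 22.
- Under the second record, any stop after Day 4 or later passes (4/5 = 80%; 3/4 = 75% fails).
- For a stop after Day 14 with misses logged up to the interruption date, three logged days pass (14/17 = 82.4%) and four fail (14/18 = 77.8%).
- With the interruption dated Day 28, any stop passes if no more than five misses are logged (23/28 = 82.1%) and fails with six (22/28 = 78.6%).
- If later misses are logged but the end date is not extended, the result can be impossible. A stop after Day 10 with 18 later misses gives (10 − 18)/10 = −80%.

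**Proposed rule.** E* = the greater of E and min(28, Week 4 visit day − 1), with 28 as the second term if there is no Week 4 visit. Made = (last treatment − first treatment + 1) − misses dated on or before the last treatment date.

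- Stop after Day 14, visit on Day 29: E* = 28 and made = 14 under all three records, so 14/28 = 50% each time.
- Dosing up to a visit on Day 26, 29 or 32: E* = 25, 28 or 31, as now.
- Treatment extended to Day 42 with 19 misses: E* = 42 and made = 23, so 23/42 = 54.8%, as now.
- Visit on Day 26 with 22 of 25 applications: 88%, as now.

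**The case against.** **The denominator follows the protocol.** Protocol 6.5 refers to the expected number for each subject, and Protocol 4.8.5 measures compliance over the drug application period. An on-treatment percentage is a legitimate description of exposure. That stands, and the figure should be kept for that purpose. It does not make the figure suitable as the only stated compliance test for PP entry.

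**SAP 11 already has a mechanism.** A latest interruption date after the last treatment date implies an unresumed stop, and E then extends to it. This stands in part: the clause works when the stop is dated to its end and all later days are logged, but the SAP requires neither.

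**Other controls may catch these subjects.** The diary records missed doses. The IP Handling Manual, which was not supplied, describes compliance determination. The deviation review before database lock (SAP 7.2) could exclude early stoppers. This limits what can be said about frequency. However, the SAP does not name early stopping as a major deviation. The limit of three consecutive misses in SAP 11 is not in the PP wording, and applying it would also depend on the days after the stop being logged.

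**A tempting stronger remedy** is to divide by 28 for every subject. The documents do not support it. SAP 3.2, footnote o, allows treatment to continue when a Day 29 visit is delayed by COVID-19. A subject with 23 applications over 42 days would then pass at 23/28 = 82.1% instead of failing at 54.8%. A Day 26 completer with 22 of 25 would fail at 22/28 = 78.6%.

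**Stronger readings a reader might infer** are that the primary result is compromised, that the PP set is substantially contaminated, or that entry is biased between arms. The primary and secondary analyses use ITT-based sets, PP carries no alpha, and the documents give no rate of early stopping, overall or by arm.

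**Conclusion.** The rule as written can give the wrong answer for PP entry. The same early stop passes or fails the 80% cut according to its record, with scores from 100% down to 50% for a stop after Day 14 and to 25% for a stop after Day 7.

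The reach is narrow. An affected subject must stop early, remain in the study, have a vIGA-AD in the Week 4 window, have no major deviation and be recorded in one of the permissive ways. The count cannot be derived and is probably small. Days on IP and missed applications are reported in any case. The point is worth correcting before unblinding, but the trial's conclusion does not turn on it.

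The verdict rests on two assumptions. First, the 80% in SAP 4.3 is the SAP 11 percentage; SAP 4.3 does not cite SAP 11, and the link is the shared term and threshold. Second, no recording rule in the IP Handling Manual already forces the third record.

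**What to change.** Before unblinding, for the PP cut and the compliance categories:

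- Set expected applications to the greater of (a) the present SAP 11 value and (b) the planned daily applications up to the day before the Week 4 visit, capped at 28, or 28 if there is no Week 4 visit.
- Set applications made to (last treatment date − first treatment date + 1) minus misses dated on or before the last treatment date.
- Keep the present percentage as a separate on-treatment exposure row beside days on IP.
- Record the change in SAP 3.5.

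One residual should be known. If the visit falls after Day 29 and an interruption is dated after Day 28, term (a) can still exceed 28. For a stop after Day 24 with a Day 32 visit, the score is 24/28 = 85.7% from the last treatment date alone but 24/31 = 77.4% with an interruption dated Day 31. With a visit on Day 29 or later, stops up to Day 22 fail however they are recorded, since 22/28 = 78.6% is the most they can score.

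The cost is SAP wording and a small derivation change, with no new data. The PP and Moderate-PP sets may be slightly smaller. Subjects who dose up to their Week 4 visit keep their present denominator, and the ITT analyses do not change.
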